9.3. Variables

Regardless of the coding system used in the database, different populations and subgroups of interest are defined as follows:

Treatment initiation with dulaglutide:

- any record of prescription of dulaglutide during the observation period without prior record of prescription of the same product in the available patient's history
- if no prior history is available to check the above criteria, the prescription is not considered as an initiation

Patients presenting with T2DM:

- with any recorded diagnosis code for T2DM
- or with any recorded treatment code for an ADM other than insulin
- or, with any recorded treatment code for insulin initiated at age >30 (defined as no record of insulin therapy during 6 months prior to first record of insulin treatment)
- or with any record of unspecified diabetes mellitus diagnosis at age >30 and without history of insulin therapy (defined as no record of insulin therapy during 6 months prior to first record of diabetes diagnosis),
- a sensitivity analysis will be conducted to determine the age threshold mentioned above (see section 9.7.3 Sensitivity analysis).

Patients with severe renal failure:

- with a recorded diagnosis of severe renal failure
- or with a recorded glomerular filtration rate (eGFR) value <30 ml/min/1.73 m²

Patients with hepatic disease:

- with a recorded diagnosis of any hepatic disorder

Patients with heart failure:

- with a recorded diagnosis of heart failure

Patients with severe gastrointestinal disease:

- with a recorded diagnosis of any of the following conditions:
 - cancer of the gastrointestinal tract,
 - diseases of the oesophagus,
 - active ulcer at the time of drug initiation (gastric, duodenal, gastro-jejunal, peptic ulcer of unspecified site),
 - active haemorrhagic gastritis, chronic atrophic gastritis, adult hypertrophic pyloric stenosis, obstruction of duodenum, and other motility disorders,
 - digestive fistula,
 - Crohn's disease, ulcerative colitis,
 - diverticular disease of the intestine,
 - severe vomiting, severe diarrhoea and severe constipation
 - motility disorders, including ileus, gastroparesis, et cetera,
 - infectious and inflammatory situations (appendicitis, cholecystitis, cholangitis).

Children and adolescents:

- Age < 18 at the time of treatment initiation
(subgroups of analysis: 0-4, 5-9, 10-14, and 15-17 years old).

Elderly:

- Age \geq 75 at the time of treatment initiation.

Pregnant and breastfeeding women:

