9.3.2. Collected variables

To assess the above subgroups and measurements of interest, several variables will be extracted from each database whenever available: demographics, medical history, treatment, clinical and clinical laboratory data on patients. These variables along with their corresponding International Classification of Disease, 10th version (ICD-10) codes are presented in this protocol (Table 9.3.2-1). For CPRD database, the corresponding Read codes will be specified in the statistical analysis plan (SAP).

Table 9.3.2-1. Variables, Subgroups and Measurements of Interest in Dulaglutide Initiators

Variable, subgroup or outcome/measurement	Definition and categories*
Patients demographics at initiation of dulaglutide use: Age Gender BMI categories, Countries	< 18, 18-44, 45-64, 65-74, ≥75 years Male or Female Weight (kg) / Height (cm) ² < 18.5, 18.5-25, 26-30, > 30 kg/m ² UK, Germany, Sweden (or Spain and France)
Co-morbidities , at initiation of treatment to identify the subgroups of interest: 
 • History of severe renal failure • Heart failure • Hepatic disease • Severe gastrointestinal disease • Children and adolescents • Elderly • Pregnant women • Breastfeeding women 	ICD-10 code N18.5, N18.5 ICD-10 codes I50, I11, I13 ICD-10 codes B18, K70-K77, C22 ICD-10 codes C15-C26 K22.0, K22.1, K22.2 -K22.6, K23-K28, K29.0, K29.4 K50, K51, K55, K57 Age < 18 (subgroups: 0-4, 5-9, 10-14, 15-17 years) Age ≥ 75 ICD-10 codes: A34, E23.0, F53, M83, O00-O99, O24.1, O24.3, O24.9, Z32-Z36, Z39 Z39.1
Lab tests values (if available): 
 • Haemoglobin A1c (HbA1c) • e-GFR • Serum Creatinine Urine albumin/creatinine ratio (UACR) 
 • LDL-C (LDL-cholesterol) • HDL-C (HDL-cholesterol) • AST/ALT • Bilirubin • Beta hCG 	Abnormal values: < 6.5%, ≥6.5% eGFR value < 30 ml/min/1.73 m ² < 120, ≥120 µmol/L or mg/dL (male) < 100, ≥100 µmol/L or mg/dL (female) UACR >30 mg/g: albuminuria present: < 1.6, ≥ 1.6 g/L < 0.35 g/L, ≥0.35 g/L ≤ 2 or > 2 times upper limit of the normal range < 2, >7mg/L Positive

Variables, Subgroups and Measurements of Interest

Variable, subgroup or outcome/measurement	Definition and categories*

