History of other medications , during 6-month baseline period	
 • ATC code or associated medcode for main pharmacological classes.
Off-Label Use	
 • Patients without T2DM • Patients with T2DM for whom dulaglutide was prescribed as first-line therapy

Variable, subgroup or outcome/measurement	Definition and categories*
T2DM	Any of the below conditions: 
 • ICD-10 code E11 • ATC codes A10P or A10X • ATC codes A10A initiated at age>30 • ICD-10 codes E14 first recorded at age>30 without ATC code A10A in the previous 6 months

Abbreviations: ALT= alanine amino transferase; AST= aspartate amino transferase; Beta hCG=Beta subunit of human chorionic gonadotrophin; BMI= body mass index; eGFR= estimated glomular filtration rate; HDL-C= high density lipoprotein cholesterol; ICD-10= International classification of disease, 10th version; LDL-C= low density lipoprotein cholesterol; T2DM= type 2 diabetes mellitus; UK= United Kingdom.

* continuous variables will be also presented by means, SD, et cetera.

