9.6. Data Management

The processes for database management will differ per country. In general, data are stored at the database level and analysed locally. The SAS Software will be used to access the raw data, manage the analytic datasets and compute data analysis.

Each database complies with local regulations in terms of data protection and record retention. The study will follow relevant chapters of European Network of Centres for Pharmacoepidemiology and Pharmacovigilance (ENCePP) and International Conference of Harmonisation ICH guidelines for data management.

Data will be checked in terms of consistency before data analysis. This is mainly due to the fact that the record of information in EHR databases is not controlled (unlike case report forms). Thus the data needs to be checked for consistency in terms of range of values, units of measurement, relevance of clinical information (for example, pregnancy for men). Some data providers, such as IMS Health, have already integrated these checks in their data production workflow, so that the checks are conducted systematically on all incoming patient records before allowing them to be integrated into the database.

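### Table 9.3.2-1 fixes one creatinine cut-off number for two units that differ about 88-fold, and its BMI classes leave out 25 to 26 and disagree with mock Table 9.7.4-1

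*Protocol*

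**What the plan says.** **Creatinine.** The laboratory rows of Table 9.3.2-1 list serum creatinine under abnormal values, with one dichotomy per sex: below 120 against 120 or more for men, and below 100 against 100 or more for women. Each number is followed by both units as alternatives. The male entry runs straight into the female one, "or mg/dL (male) < 100, ≥100", and the female entry closes the same way, "or mg/dL (female".

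**BMI.** The demographics row defines BMI as "Weight (kg) / Height (cm", squared, and gives the classes "< 18.5, 18.5-25, 26-30, > 30 kg/m"². The obesity rows of mock Table 9.7.4-1 (Section 9.7.4) instead use <18.5, 18.5-25, >25-30 and >30 kg/m².

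**Related provisions.**
- Section 9.6 says of the source data: "Thus the data needs to be checked for consistency in terms of range of values, units of measurement".
- The footnote to Table 9.3.2-1 adds that "continuous variables will be also presented by means, SD, et cetera".
- Section 9.3 defines severe renal failure by a recorded diagnosis "or with a recorded glomerular filtration rate (eGFR) value <30 ml/min/1.73 m"². Creatinine is not part of that definition.

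**The concern.** These are classification rules set in the protocol's definitions table, not detail left for later. For this table, Section 9.3.2 defers only the CPRD Read codes to the SAP.

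A threshold works only in the unit it was set for. Section 9.6 says data are in general analysed locally, by processes that differ per country, and Section 9.7.1 reports each country separately. If one database holds creatinine in µmol/L and another in mg/dL, a single number applied in both would make the share of abnormal values depend on the stored unit rather than on the patients. Table 9.4.5-1 lists creatinine among the laboratory tests available in four of the five candidate databases (all but Sweden).

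For BMI, a programmer working from Table 9.3.2-1 and one working from Table 9.7.4-1 would put some patients in different classes, or in none.

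**Working it through.** **1. Creatinine units.** The cut-offs (120 and 100) come from Table 9.3.2-1. The molar mass of creatinine, 113.12 g/mol, is a physical constant that the protocol does not give and is taken as known.

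- 1 mg/dL = 10 mg/L = 10,000 / 113.12 µmol/L = 88.4 µmol/L.
- Cut-offs read as µmol/L: 120 × 113.12 / 10,000 = 1.36 mg/dL; 100 × 113.12 / 10,000 = 1.13 mg/dL.
- Cut-offs read as mg/dL: 120 × 10,000 / 113.12 = 10,608 µmol/L; 100 × 10,000 / 113.12 = 8,840 µmol/L.

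The stated numbers therefore cannot be reproduced as one cut-off in two units. The mg/dL reading sets the threshold about 88 times higher than the µmol/L reading. A man at exactly 120 µmol/L would be stored as 1.36 in a mg/dL database and classed as below 120.

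**2. BMI classes.** Both sets of classes were applied to a grid in steps of 0.1 from 15.0 to 49.9.

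| Table | Values without a class |
|---|---|
| 9.3.2-1 (18.5-25, 26-30, >30) | 25.1 to 25.9 |
| 9.7.4-1 (18.5-25, >25-30, >30) | none |

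Rounding BMI to whole numbers does not reconcile the tables. The 18.5 boundary presupposes at least one decimal, and rounding 25.1-25.4 down to 25 would place those values in 18.5-25, whereas Table 9.7.4-1 places them in >25-30.

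**3. Share of patients in the gap.** The protocol gives no BMI distribution, so a normal distribution with mean m and SD s is assumed: P(25 < BMI < 26) = Φ((26 − m)/s) − Φ((25 − m)/s).

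| Assumed mean | Assumed SD | Share in gap |
|---|---|---|
| 30 | 5 | 5.3% |
| 32 | 6 | 3.7% |
| 34 | 6 | 2.4% |
| 36 | 6.5 | 1.7% |

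**4. BMI formula.** For an illustrative patient of 80 kg and 170 cm, the formula as printed gives 80 / 170² = 0.0028. In metres, 80 / 1.70² = 27.7. Only the second figure is on the scale of the printed classes.

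**5. Where the variables are used.** Creatinine appears in no subgroup definition in Section 9.3 and has no row in mock Table 9.7.4-1 as shown. BMI has rows in that table and is descriptive only.

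**The case against.** The best case for leaving this alone is that nothing important depends on it and that ordinary care would catch it.

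- **Checks.** Section 9.6 plans checks of ranges as well as units, and creatinine values near 1 against a cut-off of 120 should stand out. The means and SDs promised in the footnote would also reveal the unit. Section 9.8 has programs validated by two people, and under Section 9.7.5 the SAP will describe and justify variation among countries.
- **BMI.** The table that reports BMI has no gap, and the kg/m² label in the same cell shows that cm is a slip.

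Much of this stands. It makes an unnoticed error less likely and limits what it could damage. It does not make the rule right: Section 9.6 names no target unit and no conversion, and the definition it would be checked against accepts both units at the same number. Summary means and SDs do not repair the categories. Table 9.7.4-1 cannot simply be taken to override the definitions table, because its own note says its structure may change in the final report.

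A reader might also infer three stronger things that the documents do not support.

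- **Renal classification between countries.** The protocol does not make creatinine a substitute for a missing eGFR. Section 9.9.1 says only that eGFR may not be recorded properly and that false negatives may follow. Nor does the protocol say which databases store mg/dL, so a distorted comparison between countries is conditional, not established.
- **All patients in the lowest BMI class.** This would need someone to compare a value near 0.003 with a cut-off of 18.5, which is not realistic.
- **A known share of patients without a BMI class.** Any percentage rests on an assumed distribution.

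**Conclusion.** Wrong as written, with limited effect. The creatinine rule gives the same number to two units that differ by a factor of about 88.4. Applied literally to mg/dL data, it would flag practically nobody. That consequence holds only if a selected database stores mg/dL and the values are not converted first, and the protocol settles neither.

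The BMI classes of Table 9.3.2-1 omit values between 25 and 26 and contradict Table 9.7.4-1. The affected share is about 1.7% to 5.3% of patients with a recorded BMI, assuming a normal distribution with mean 30 to 36 and SD 5 to 6.5. Sweden, which has no BMI data, is not affected. The height unit is an editorial slip.

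No eligibility rule, subgroup definition, off-label classification or medication-error classification depends on any of the three. The exposure is confined to descriptive summaries of creatinine and BMI.

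**What to change.** In Table 9.3.2-1:

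1. Convert all creatinine values to µmol/L before classification and state the cut-offs in that unit only. Alternatively, print the equivalent for each unit: 120 µmol/L (1.36 mg/dL) for men and 100 µmol/L (1.13 mg/dL) for women. This takes µmol/L as the intended unit, since only that reading gives a usable split; the sponsor should confirm it.
2. Write the BMI formula with height in metres.
3. Replace the BMI classes by <18.5, 18.5-25, >25-30 and >30 kg/m², so that they match Table 9.7.4-1.

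The cost is an edit to one table and one unit-conversion step in the programs of any database that stores mg/dL. No additional data are needed.

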- Any record of pregnancy or breast feeding at the time of treatment initiation.

Patients with medication errors:

- Prescribed and/or administered > 1 dose per week of dulaglutide (6).
- The number of doses/week will be calculated by measuring the time span between the current prescription and the next one (in weeks) and dividing the number of injections prescribed in the current prescription by this time span. This number of doses/week will be used in the cross sectional study as an attribute of the prescription to assess the occurrence of medication errors as described above.

Patients with off-label use:

- Prescribed dulaglutide with no diagnosis of T2DM as defined above, at the beginning of this list of subgroups of populations.
- Prescribed dulaglutide with a diagnosis of T2DM as defined above and without a record of other ADMs during the 6-month baseline period, i.e. dulaglutide was prescribed as first-line therapy.

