
Other comorbidities frequent in T2DM patients: Dyslipidemia Hypertension
 
Macrovascular complications: Ischaemic heart disease
 
Stroke Peripheral arterial obstructive disease
 
Microvascular complications: Diabetic neuropathy Diabetic retinopathy Diabetic nephropathy
	
ICD-10 codes E78 or lipid modifying agents (ATC C10) ICD-10 codes I10-I15 or antihypertensives (ATC C02, C03, C04, C07, C08, C09) with no angina pectoris (I20, I25)
 
ICD-10 codes I20-I25 or antiangina agents (ACT C01D, C07, C08, C09) I61-I64 I70.2
 
G62.9 H36.0 N08.3

Solid tumours (Cancer)
 
 • liver • pancreas • endometrium • colon • rectum • breast • bladder 	
ICD-10 codes C220-C229 ICD-10 codes C250-C259 ICD-10 code C541 ICD-10 codes C182-C189 ICD-10 code C20 ICD-10 codes C500-C509 ICD-10 codes C670-C679

Dulaglutide dose: per 0.5 ml
	
Dose: 0.75 mg / week 1.5 mg / week >1.5 mg / week

Variables, Subgroups and Measurements of Interest

Variable, subgroup or outcome/measurement	Definition and categories*
Concomitant medications for T2DM , at index date of dulaglutide initiation	
 • Molecule: INN/brand name • ATC code or associated medcode for AMD 
A10A Insulins and analogues
 
 ○ A10AB Insulins and analogues for injection, fast-acting ○ A10AC Insulins and analogues for injection, intermediate-acting ○ A10AD Insulins and analogues for injection, intermediate- or long-acting combined with fast-acting ○ A10AE Insulins and analogues for injection, long-acting ○ A10AF Insulins and analogues for inhalation 
A10B Blood glucose lowering drugs, excluding insulins
 
 ○ A10BA Biguanides ○ A10BB Sulfonylureas ○ A10BD Combinations of oral blood glucose lowering drugs ○ A10BF Alpha glucosidase inhibitors ○ A10BG Thiazolidinediones ○ A10BH Dipeptidyl peptidase 4 (DPP-4) inhibitors ○ A10BX Other blood glucose lowering drugs (exenatide, liraglutide, lixisenatide, albiglutide), excluding insulins 
A10P SGLT2 Inhibitors

Other concomitant medications , at index date of dulaglutide initiation	
 • ATC codes or associated medcode for main pharmacological classes.
History of medications for T2DM , during 6-month baseline period	
 • ATC code or associated medcode for anti-diabetes medications (see above)

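### Table 9.3.2-1 counts any C07, C08 or C09 prescription as ischaemic heart disease, so that row will largely track antihypertensive use; its heart failure and pregnancy codes also need narrowing to fit section 9.3

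*Protocol*

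**What the plan says.** All code lists are in Protocol Table 9.3.2-1 (section 9.3.2). That section presents the ICD-10 codes as part of the protocol and leaves only the CPRD Read codes to the SAP.

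- **Ischaemic heart disease:** "ICD-10 codes I20-I25 or antiangina agents (ACT C01D, C07, C08, C09". The two limbs are joined by 'or', so a prescription alone is enough.
- **Hypertension, same table:** "ICD-10 codes I10-I15 or antihypertensives (ATC C02, C03, C04, C07, C08, C09) with no angina pectoris (I20, I25".
- **Heart failure:** the table gives "ICD-10 codes I50, I11, I13"; section 9.3 defines the subgroup as patients "with a recorded diagnosis of heart failure".
- **Pregnancy and breastfeeding:** the table gives "ICD-10 codes: A34, E23.0, F53, M83, O00-O99, O24.1, O24.3, O24.9, Z32-Z36, Z39 Z39.1"; section 9.3 asks for "Any record of pregnancy or breast feeding at the time of treatment initiation".

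Ischaemic heart disease is a row of the primary-objective mock table (Table 9.7.4-1), reported for all initiators and for every subgroup. Heart failure, and pregnant and breastfeeding women, are themselves subgroups of the primary objective.

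**The concern.** Three of the four drug classes that suffice for ischaemic heart disease are described one row earlier as treatments for hypertension. The hypertension row sets aside patients with an angina code, so the overlap was noticed there. The ischaemic heart disease row has no matching restriction. The primary objective is to characterise initiators by their main co-morbidities, and a reader of the report would take this row as cardiac disease when much of it may be treated hypertension.

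For heart failure and pregnancy the question is who enters the subgroup. A code list wider than the text definition alters every characteristic reported for that subgroup, as well as its size.

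Nothing else in the protocol catches this. The only sensitivity analysis (section 9.7.3) concerns the age threshold in the type 2 diabetes definition used for off-label use. The misclassification example in section 9.9.1 deals with missed cases of severe renal failure. False positives from drug proxies or broad codes are not discussed.

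**Working it through.** The protocol states no prevalence for these conditions, so there is no figure to reproduce. The check compares the definitions and then shows what they imply over assumed ranges.

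**1. Ischaemic heart disease**

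Take a patient with a C09 prescription and no I20-I25 code.
- Hypertension row: C09 is listed and there is no I20 or I25 code, so the patient is counted.
- Ischaemic heart disease row: C09 is listed and no diagnosis is needed, so the patient is counted.

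The same holds for C07 and C08. Of the four classes in the ischaemic heart disease rule, only C01D is absent from the antihypertensive list.

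Let p be the true prevalence and q the share of patients without the disease who have a C07, C08 or C09 prescription. If all true cases are captured:

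reported = p + (1-p)q, and excess = (1-p)q.

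Both inputs are assumptions: p 10-30%, q 40-80%.

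| p | q | reported | excess | ratio to p | share of counted patients who are true cases |
|---|---|---|---|---|---|
| 10% | 40% | 46% | 36 points | 4.6 | 22% |
| 10% | 80% | 82% | 72 points | 8.2 | 12% |
| 20% | 60% | 68% | 48 points | 3.4 | 29% |
| 30% | 40% | 58% | 28 points | 1.9 | 52% |
| 30% | 80% | 86% | 56 points | 2.9 | 35% |

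Section 9.5.1 aims for a precision of ±10% in the smallest country. The smallest excess in the table is 28 points. With p = 20%, the excess stays below 10 points only if q is below 0.10/0.80 = 12.5%. The conclusion therefore does not depend on the upper end of the range.

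**2. Heart failure**

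Section 9.3 requires a heart failure diagnosis. The table takes the whole of I11 and I13, both of which lie inside the range I10-I15 that the protocol uses for hypertension. The overlap shows that the table is wider than the text. That these categories also hold hypertensive disease without failure comes from ICD-10, which the protocol adopts but does not reproduce.

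If h is the true prevalence and g the share of the others with a non-failure I11 or I13 code, reported = h + (1-h)g. Both inputs are assumed:
- h = 3%, g = 1%: 0.03 + 0.97 × 0.01 = 4.0%
- h = 3%, g = 10%: 0.03 + 0.97 × 0.10 = 12.7% (ratio 4.2)
- h = 10%, g = 1%: 0.10 + 0.90 × 0.01 = 10.9% (ratio 1.1)
- h = 10%, g = 10%: 0.10 + 0.90 × 0.10 = 19.0%

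**3. Pregnancy**

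Under ICD-10, E23.0 is hypopituitarism and M83 is adult osteomalacia, of which only one subcode is puerperal. Let s be the share of true pregnancies recorded and f the share of other patients caught by the extra codes. Then reported = s·p + (1-p)f, with assumed p of 0.1-0.3% and f of 0.02-0.3%:
- complete recording (s = 1): the ratio of reported to true runs from 1.07 to 4.0
- s = 30-60%: the ratio runs from 0.37 to 3.6

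The direction of the net error is therefore not determined.

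**The case against.** **Drug proxies have a purpose.** Section 9.9.1 warns that diagnoses will be missing for some patients, especially in primary care. Swedish diagnoses come only from specialist and hospital care (section 9.4.3). A diagnosis-only rule would miss cases. This stands as a reason to keep a proxy, but not one made of classes that the same table calls antihypertensives.

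**The consequence for ischaemic heart disease is bounded.** It is one descriptive row. It defines none of the nine subgroups and does not affect off-label use, medication errors or study size. This stands, and the size of the excess rests wholly on assumed inputs.

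**The text definitions in section 9.3 are sound.** For heart failure and pregnancy the fault is a table broader than the text, so the two need aligning. This is accepted, and those parts are put that way here.

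**There is still a chance to correct the list.** The feasibility step checks the validity of each variable (section 9.5.2), and the SAP is finalised afterwards (section 9.7.5). That gives an opportunity; it does not repair the written rule.

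**A stronger reading of the pregnancy codes.** A reader might infer that pregnancy prevalence will be inflated, or that most of the subgroup will be false positives. The protocol does not support either. Pregnancy and breastfeeding data are described as very limited in all five countries (Table 9.4.5-1), so the net figure could be too low, and nothing in the protocol says how often the extra codes occur. Section 9.6 already foresees a consistency check for pregnancy recorded in men; women who are not pregnant but carry these codes would still pass it.

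**Conclusion.** The ischaemic heart disease definition is wrong as written, and this is visible in the table itself. Over the assumed ranges the row would show 46-86% where the truth is 10-30%. The real size cannot be derived from the protocol, but the direction is clear whenever C07-C09 use is common among patients without the disease.

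The heart failure point also holds, as a mismatch between table and text that changes membership of a primary-objective subgroup. Its illustrative effect runs from slight (10.9% against 10%) to large (12.7% against 3%).

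The pregnancy point holds with lower confidence, since it depends on what the ICD-10 codes mean. It is limited to this: the extra codes can add women who are not pregnant to a very small subgroup.

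**What to change.** Edit Table 9.3.2-1 before data extraction:

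- **Ischaemic heart disease:** I20-I25 or C01D only. If the broad rule is wanted, particularly for Sweden, report it as a separate, labelled sensitivity row.
- **Heart failure:** I50 and only those subcodes of I11 and I13 that specify heart failure, so that the table matches section 9.3.
- **Pregnancy:** drop E23.0 and limit M83 to its puerperal subcode.

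Carry the same restrictions into the Read code lists for CPRD. The cost is a code-list edit. The downside is that some patients with ischaemic heart disease who have neither a recorded diagnosis nor a C01D prescription will be missed, notably in Sweden; the sensitivity row would show how much the choice of rule matters.

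### The colon tumour row in Table 9.3.2-1 starts at C182 and omits C180 and C181 without a stated reason, so the descriptive colon cancer row is under-counted.

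*Protocol*

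**What the plan says.** Table 9.3.2-1 in protocol Section 9.3.2 has a block for solid tumours that lists seven sites, with seven code entries in the same order. Colon is the fourth and is given as "ICD-10 codes C182-C189". Rectum is the fifth and is given as "ICD-10 code C20". The other rows with several codes are liver ("ICD-10 codes C220-C229"), pancreas ("ICD-10 codes C250-C259"), breast ("ICD-10 codes C500-C509") and bladder ("ICD-10 codes C670-C679"). Endometrium is a single four-character code, C541.

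The ICD-10 codes are fixed in the protocol itself. The only coding that Section 9.3.2 leaves for later concerns the UK: "For CPRD database, the corresponding Read codes will be specified in the statistical analysis plan (SAP"). Section 9.7.5 says that the SAP will be based on the protocol.

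The mock table for the primary objective (Table 9.7.4-1) reports colon and rectum as separate lines, for each subgroup and for all initiators. Section 9.7.1 makes the analysis purely descriptive, by country and by year, with no pooling.

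**The concern.** Colon is the only multi-code tumour row that does not begin at .0. A programmer who applies the table literally will leave out any patient whose only colon tumour code is C180 or C181, and no other line of the mock table will pick that patient up. According to Table 9.4.5-1, four of the five candidate databases record diagnoses in ICD-10, so the range would be programmed as printed in any of those four that is selected. The same shortfall would then recur in each such country and in each annual wave.

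There is also a possible effect on comparability. CPRD uses Read codes. If these are mapped from the label colon rather than from the printed range, the UK row will cover a wider set of tumours than the same row elsewhere.

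What is at stake is the accuracy of one line in the description of comorbidity. No estimate, test or subgroup definition is built on it.

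**Working it through.** The protocol gives no figure for this row to reproduce. The check is a comparison of code sets, all taken from Table 9.3.2-1.

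**Step 1: the range itself.** The full set of fourth-character codes, C180 to C189, has 10 members. The printed range, C182 to C189, has 8. The difference is 10 − 8 = 2 codes: C180 and C181.

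**Step 2: the other multi-code rows.**

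| Row | Printed range | Codes in range | Starts at |
|---|---|---|---|
| Liver | C220-C229 | 10 | .0 |
| Pancreas | C250-C259 | 10 | .0 |
| Breast | C500-C509 | 10 | .0 |
| Bladder | C670-C679 | 10 | .0 |
| Colon | C182-C189 | 8 | .2 |

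**Step 3: does another tumour row catch the omitted codes?** Each code is tested against all seven rows.

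- C180: in none.
- C181: in none.
- C19: in none. It is outside the colon range and outside the rectum entry, which is C20 alone.
- C20: in the rectum row, as expected.

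**Step 4: direction.** Codes are left out of the row and none are wrongly added, so the colon count can only be too low. A patient with C180 or C181 who also has a code from C182 to C189 is still counted. The loss is limited to patients with no colon code other than the two omitted ones.

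**Step 5: size.** With N initiators, prevalence p of colon cancer, and share m of those patients coded only C180 or C181, the number missed is N × p × m. The documents give neither p nor m. For scale only, assume p between 0.5% and 2% and m between 5% and 30%; neither range comes from the documents.

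- Per 1,000 initiators: from 1,000 × 0.005 × 0.05 = 0.25 to 1,000 × 0.02 × 0.30 = 6 patients.
- In a country at the 100-patient minimum of Section 9.5.1: from 0.025 to 0.6 patients.

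These figures show that the count involved is small under such assumptions. They do not estimate the loss in this study.

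**The case against.** The strongest reply is that the omission may be intended. The table does choose a single four-character code for endometrium, so its authors sometimes work below the three-character level, and a narrow reading of colon is conceivable. That stands in part: the text shows that the codes are missing, but not that they were left out by mistake. If the choice was deliberate, however, the protocol should say so. With four full ranges beside it and no explanation, a reader cannot tell.

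It can also be said that the row is descriptive, and that Section 9.9.1 already warns that some diagnoses will be missing or wrongly reported. This limits the importance of the point. It does not excuse a gap in the definition itself, which adds to any under-recording in the data.

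Three stronger readings are tempting, and the documents do not support them.

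- A reader might infer that the plan under-counts colorectal cancer as a whole. It has no such measure: colon and rectum are separate rows with no combined line. The absence of C19 is a gap between two chosen sites, not an error in the colon range.
- A reader might infer that the tumour rows contradict the severe gastrointestinal disease subgroup, which uses "ICD-10 codes C15-C26". The protocol never says that the two should reconcile, and they could not. C15-C17, C21, C23, C24 and C26 also lie in that range and have no tumour row, so patients with those codes would enter the subgroup without a tumour line whatever the colon code.
- A reader might attach a percentage loss to the colon row. That needs a split of cases by code, which the documents do not contain.

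**Conclusion.** The point holds as a minor defect of definition. As printed, the colon row leaves out C180 and C181 without explanation, and its count is biased downwards by an amount that cannot be computed from the documents. The conclusion assumes that the row is meant to cover the colon category as fully as the liver, pancreas, breast and bladder rows cover theirs, and that some patients carry only the omitted codes. The gap at C19 is secondary: it leaves a code unassigned between two rows.

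Nothing else is affected. Membership of the severe gastrointestinal disease subgroup, off-label use, medication errors and study size do not depend on the colon row.

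**What to change.** In Table 9.3.2-1, change the colon entry to C180-C189, or keep the present range and state why .0 and .1 are excluded. Assign C19 to one named row and say which; the documents do not favour one placement over another. Use the same definitions when the CPRD Read codes are specified in the SAP, so that the colon and rectum rows mean the same thing in every country.

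The cost is an edit to one or two entries of one table. No extra data, variables or analyses are needed. It is cheapest before the extraction programs are written; after that, the affected rows would have to be rerun for each country and wave already reported.
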